## **Schematic Diagram of Trial Design**

## 7.4 Study Variables

### 7.4.1 Primary Endpoints

The relationship between the observed cerebral oximetry data and a number of predefined intraoperative and postoperative clinical variables will serve as the primary endpoints of this trial. The clinical variables will include the following intraoperative and postoperative (PACU or initial 12 hours of the ICU stay) parameters:

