  - AUCSpO2 < 80% regardless of intraoperative FiO2 values ○
  - AUCSpO2 < 75% regardless of intraoperative FiO2 values ○
  - AUCSpO2 < 70% regardless of intraoperative FiO2 values ○
- Use of any intraoperative, intravenous vasopressor and/or inotropic agent (as assessed by amount of time in minutes on any IV drug support regardless of dose and assessed by total dose of drug delivered to patient)
- Intraoperative urine output in any patient with an indwelling foley catheter as assessed by mLs urine/kg/hr for total time in operating room
- Need for intraoperative red blood cell transfusion (as assessed by number of RBC units transfused)
- Observed desaturation prompted change in surgical procedure (e.g., the surgery was paused to inflate the collapsed lung to improve systemic tissue oxygenation) ●  
● Occurrence of any intraoperative stroke or transient ischemic attack (as assessed by documented clinical neurological assessment or cerebral imaging study) ● Any

observed intraoperative myocardial ischemia or infarction (as assessed by intraoperative ECG changes and/or myocardial biomarkers (i.e. troponin increase)

- ❶ Area under the curve of any observed intraoperative hyperglycemia ( $AUC_{Glu} > 110 \text{ mg/dL}$ ) in patients with a documented history of either type I or II diabetes mellitus ❶ Any occurrence of intraoperative atrial fibrillation (capturing duration of atrial fibrillation and whether treatment was required)
- ❶ Total time spent in operating room
- ❶ Total amount of narcotic administered in the operating room
- ❶ Total volume of crystalloid administered in the operating room
- ❶ Total volume of colloid administered in the operating room
- ❶ Anti-emetic medications administered in the operating room
- ❶ Surgical procedure performed
- ❶ Time on single lung ventilation ❶

Intraoperative Use of epidural catheter

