$AUC_{SpO_2} < 75\%$  regardless of intraoperative  $FiO_2$  values

$AUC_{SpO_2} < 70\%$  regardless of intraoperative  $FiO_2$  values

- Time from procedure completion to arrival in the post anesthesia care unit (PACU) or ICU
- Temperature upon PACU/ICU arrival
- Aldrete score upon PACU/ICU arrival and at 30 & 60 (or at discharge) min post-PACU arrival (See Appendix A)
- Any occurrence of immediate postoperative atrial fibrillation
- Any myocardial ischemia in the immediate postoperative period
- Any need for allogeneic RBC transfusion in the immediate postoperative period
- Any observed stroke or TIA in the immediate postoperative period
- Time to clinical readiness for PACU discharge as assessed by established institutional discharge criteria (see Appendix B)
- Frequency and severity of nausea and vomiting observed in the PACU and/or ICU as assessed by an accepted postoperative nausea and vomiting scale
- ICU length of stay (ICU-LOS) [anticipated to be at least 10-20 evaluable subjects for this parameter if 100 patients are enrolled] which will be defined as time to clinical readiness for ICU discharge as assessed by the clinical team caring for the patient
- Postoperative mechanical ventilation time if still intubated and admitted to the ICU following the surgical procedure
- Use of any immediate postoperative, intravenous vasopressor and/or inotropic agent (as assessed by amount of time in minutes on any IV drug support regardless of dose and assessed by total dose of drug delivered to patient)
- Immediate postoperative urine output in any patient with an indwelling foley catheter as assessed by mLs urine/kg/hr for total time in operating room
- Hospital length of stay (H-LOS)
- Need for skilled nursing facility/rehabilitation hospital admission upon discharge from index hospitalization
- Length of time spent in a skilled nursing facility/rehabilitation hospital upon discharge from index hospitalization if a relevant data point for each subject

- Need for hospital readmission for any reason within 30 days of surgical procedure
  - Observed change from preoperative baseline Mini-mental Status Examination (MMSE) score (including postoperative day #1 and postoperative day #3 or discharge scores)
  - Presence/absence of postoperative delirium (as assessed by the CAM Delirium assessment tool results obtained preoperatively and postoperatively upon PACU discharge, Day#1 and 3 [or hospital discharge])

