- Change in baseline renal function (as assessed by  $\Delta$ GFR from baseline compared to inhospital nadir postoperative GFR estimated by the Cockcroft-Galt method,  $\Delta$ preoperative serum creatinine obtained within 6 weeks of surgical procedure to nadir postoperative value and any new need for any form of renal replacement therapy)
- Postoperative use of epidural catheter
- Documented return of bowel function time (as assessed by time to first bowel movement following surgical procedure)
- Need for postoperative (any time from transfer from OR to discharge) red blood cell transfusion (as assessed by number of RBC units transfused)
- Occurrence of any postoperative (any time from transfer from OR to discharge) stroke or transient ischemic attack (as assessed by documented clinical neurological assessment or cerebral imaging study)
- Any observed postoperative (any time from transfer from OR to discharge) myocardial ischemia or infarction (as assessed by physical examination, intraoperative ECG changes and/or myocardial biomarkers [i.e. troponin increase])
- Postoperative (any time from transfer from OR to discharge) occurrence of any form infectious complication up to POD 30
- Postoperative time to wean from supplemental oxygen
- Postoperative (any time from transfer from OR to discharge) composite endpoint that includes any subject with at least one of the following: new onset atrial fibrillation,  $\geq$ Grade 2 PONV, HLOS $\geq$ 4.5 days, PACU LOS $\geq$ 2 hours, any infectious complication, death, stroke, myocardial infarction, greater 0.5 mg/dL increase in creatinine or new need for renal dialysis, postoperative need for intravenous inotropes or vasoactive medications

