### **11.1.3 Preoperative Variables Collected**

Following finalization of informed consent the patient's chart will be reviewed to ensure that they are appropriate for participation based upon the study's inclusion and exclusion criteria.

Additionally, the patient's records will be reviewed and key demographics and clinical variables will be collected using a standardized data collection tool. 11.1.3.1 Demographics and clinical variables collected

Age	+/- Recent MI
Gender	+/- CHF
Race	+/- DM Type II (insulin)
Height	+/- DM Type II (non-insulin)
Weight	+/- Renal Insufficiency
BMI	+/- COPD
Serum creatinine	+/- OSA
Hemoglobin	+/- Dementia
LVEF	+/- Alcohol use
+/- Vascular disease	+/- Tobacco use
+/- Stroke/TIA	+/- Illicit drug use
+/- CAD	

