#### 11.3.3.2 Immediate Postoperative Clinical Variables Collected

Vasopressor use	Antiemetic medication administered
Inotrope use	Total crystalloid administered
Urine output	Total colloid administered
Myocardial ischemia	Temperature on arrival
Stroke or TIA	Aldrete score (arrival, 30 & 60 min)
Hyperglycemia $AUC_{Glu} > 110$	PONV Severity
Atrial fibrillation	Time to PACU d/c readiness
Time spent in PACU/ICU	Time on mechanical ventilation
Amount of narcotic administered	

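### Three postoperative endpoints are misdefined or cannot be fully observed as written: creatinine change runs to the nadir, postoperative urine is tied to operating-room time, and the follow-up call can come before day 30

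*Combined protocol and SAP*

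**What the plan says.** All three items are in the postoperative list of section 7.4.1.2, part of the variables that section 7.4.1 introduces under primary endpoints.

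- **Renal function.** Creatinine change is taken from preoperative "serum creatinine obtained within 6 weeks of surgical procedure to nadir postoperative value". The same bullet compares baseline GFR with the "inhospital nadir postoperative GFR estimated by the Cockcroft-Galt method". The composite at the end of the list counts a "greater 0.5 mg/dL increase in creatinine or new need for renal dialysis" as an event, at any time from leaving the operating room to discharge.
- **Urine.** The postoperative bullet reads "Immediate postoperative urine output in any patient with an indwelling foley catheter as assessed by mLs urine/kg/hr for total time in operating room". The intraoperative bullet in section 7.4.1.1 reads "Intraoperative urine output in any patient with an indwelling foley catheter as assessed by mLs urine/kg/hr for total time in operating room". Section 7.4.1 describes the variables as "intraoperative and postoperative (PACU or initial 12 hours of the ICU stay) parameters". Section 11.3.3.2 lists urine output and "Time spent in PACU/ICU" together. Weight is in the preoperative list of section 11.1.3, where "key demographics and clinical variables will be collected using a standardized data collection tool".
- **Thirty-day events.** Section 7.4.1.2 sets readmission at 30 days from surgery. It gives infection two windows in one bullet, one ending at discharge and one at POD 30. Section 7.2.4 ends follow-up at the telephone interview at 4 weeks, and section 11.4.4 allows 5 days either side. The synopsis (Duration of Treatment) calls it a 30 day interview. The call items in section 11.4.4 are general well-being, readmission or emergency visits, and days in a nursing or rehabilitation facility. Infection is not named.

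**The concern.** Section 6.2 says that the pilot is to identify the outcome variables worth carrying into a larger trial. A variable computed in the wrong direction, over the wrong period or with incomplete follow-up may be dropped or kept for the wrong reason.

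Section 15 gives general tests and corrects none of these definitions. For the creatinine and urine variables the analyst must either follow the text and obtain wrong values, or redefine the endpoint once the data are in. For the 30-day events the loss is of another kind: what happens after an early call is not recorded by any planned route.

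**Working it through.** The plan gives no figure of its own on these points, so there is none to reproduce. The checks are direct.

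**(a) Creatinine.** Assumed, for illustration: baseline 1.0 mg/dL; postoperative values 0.9, 1.8, 1.2.

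- As written, to the nadir: 0.9 - 1.0 = -0.1 mg/dL.
- To the peak: 1.8 - 1.0 = +0.8 mg/dL.
- Cockcroft-Gault GFR is inversely proportional to creatinine when age, sex and weight are fixed. Nadir GFR therefore comes from the peak creatinine: 1.0/1.8 - 1 = -44%.

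So one bullet reports a slight improvement and a 44% fall for the same subject. The error needs at least two postoperative values. Table 1 schedules creatinine in follow-up but does not say how many draws. Because nadir GFR already requires the peak creatinine, the correct change can be derived from planned data.

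**(b) Urine.** Operating-room time is the wrong period whether it is read as the denominator or as the observation window. Under the denominator reading:

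recorded rate = true rate x (postoperative hours / operating-room hours)

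The 12 h ICU period is in the plan. The 2 h in PACU and the operating-room hours are assumed.

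| Operating-room hours | Factor, 2 h in PACU | Factor, 12 h in ICU |
|---|---|---|
| 2 | 2/2 = 1.0 | 12/2 = 6.0 |
| 4 | 2/4 = 0.5 | 12/4 = 3.0 |
| 6 | 2/6 = 0.33 | 12/6 = 2.0 |

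Two subjects with the same true rate and the same operating-room time would differ by 12/2 = 6-fold according to where they recovered. Section 7.4.1.2 anticipates at least 10 to 20 ICU subjects among 100, so both kinds will be present.

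**(c) Call.** Target 4 x 7 = day 28. Window: 28 - 5 = day 23 to 28 + 5 = day 33, which is 11 permitted days. Days 23 to 29, which are 7 of the 11 and include the target, precede day 30. Uncovered time is 30 - 28 = 2 days at the target and 30 - 23 = 7 days at the earliest call. Adverse-event monitoring in Table 1 is another route for infection, but it covers the same follow-up period, which ends at the call.

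**The case against.** The best defence is that these are visible slips in a long list of exploratory variables. Nadir may have been meant as worst function, the urine phrase is plainly carried over from the intraoperative bullet, and the synopsis already gives 30 days for the call. That is fair as to intent, and it limits the weight of the point. It does not settle the text. Two readings of the creatinine bullet give opposite signs, and the synopsis conflicts with sections 7.2.4, 11.4.1 and 11.4.4.

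A reader might also infer more than the documents support:

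- *That the renal signal is lost.* It is not. GFR in the same bullet runs in the right direction, and the composite counts an increase.
- *That the composite is corrupted.* Its creatinine component does not refer to a nadir. It asks for an increase within a window from operating-room transfer to discharge, so the illustrative subject already qualifies on the natural reading. That window also closes before the call, so call timing does not affect it.
- *That the urine rule costs a known amount of power or inflates false positives.* Any such figure needs assumed rates, spreads, effect size and catheter use, and applies only to the denominator reading. Bias needs operating-room or postoperative time to differ by arm, and the documents give no figures for that.
- *That data already planned repair all three.* They do not repair the call: a day 23 interview says nothing about days 24 to 30.
- *That the early call favours one arm.* Nothing suggests it. Any loss is expected in both.

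**Conclusion.** The point holds as a correction of definitions and of one schedule item, and it should be made.

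- The creatinine change can have the wrong sign whenever a subject has two or more postoperative values. The -0.1 against +0.8 mg/dL is illustrative.
- The urine rate is taken over the wrong period. As a denominator, the error is the ratio of postoperative to operating-room hours, 0.33 to 6.0 over the assumed range. This mainly adds noise.
- The 30-day endpoints are not fully observed on 7 of 11 permitted call days, by 1 to 7 days. Event timing is not given, so the share missed is unknown.

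The third item matters most for timing of the amendment, because no planned source recovers those days later. The arithmetic on days uses only the plan's own figures; the creatinine values, operating-room hours and PACU hours are assumptions.

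**What to change.** - **Creatinine (7.4.1.2).** Replace the postoperative nadir with the peak in-hospital postoperative creatinine. Naming the same value in the composite's component is a clarification only. No new data are needed.
- **Urine (7.4.1.2).** Divide urine collected in PACU, or in the first 12 ICU hours, by weight and by the catheterised hours observed in that same period. Urine output, PACU/ICU time and weight are already collected. The form needs the 12-hour cut for ICU subjects and the time of catheter removal.
- **Call (11.4.4).** Place it on or after day 30, for example days 30 to 35. Ask for dates of readmission and of infection, and count events through day 30. Give infection one window. Align the synopsis and sections 7.2.4, 11.4.1 and 11.4.4.
- **Clerical.** The postoperative ischemia bullet in 7.4.1.2 refers to intraoperative ECG changes; it should refer to postoperative ones.

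The cost is protocol and case-report-form wording, a call a few days later, two dated questions and the two urine items. It needs no new visits or tests.

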Active testing of this technology over the past decade has brought forth the concept that by placing the sensors over the frontal lobe cerebral tissue and actively working to reverse the observed desaturations clinicians are very likely protecting the oxygen balance in all of the body's vital organs by using the brain as an index organ of adequate perfusion and oxygenation. (Grocott HP) Indeed, the improved clinical outcomes that have been published in the peer reviewed literature suggest a diffuse effect of generalized organ protection (e.g., decreased hospital LOS, decreased ICU LOS, decreased STS MOMM). It appears that despite the regional nature of the small amount of tissue that is monitored (i.e. 15 mm^3 of frontal lobe cortical gray matter) that this highly metabolically active cerebral tissue may be the most desirable tissue to assess and use as an index organ for providing adequate oxygen balance in the rest of the body.

Clinicians caring for perioperative cardiac surgical patients (e.g., cardiac anesthesiologists, cardiac surgeons and perfusionists) were early adopters of this technology related to the compromised cardiovascular status inherent to their patient population and the complex nature of the surgical procedures they perform (e.g., extracorporeal circulation and deep hypothermic circulatory arrest).

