#### 11.4.4 Postoperative 4 Week Telephone Interview

At 4 weeks (+/- 5 days) from the day of the surgical procedure a study team member will make a telephone call to the subject with the goal of assessing overall well being, if there was any need for hospital readmission or emergency ward visit, and if applicable how many days the subject remained in a skilled nursing facility or rehabilitation hospital.

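### Stroke/TIA, MI, transfusion and the composite's clinical components are counted only to discharge, so a shorter stay would leave the intervention arm less time to score events

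*Combined protocol and SAP*

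**What the plan says.** Section 7.4.1.2 ties several postoperative endpoints to discharge. The composite reads "Postoperative (any time from transfer from OR to discharge) composite endpoint that includes any subject with at least one of the following", stroke reads "Occurrence of any postoperative (any time from transfer from OR to discharge) stroke or transient ischemic attack", and the cardiac endpoint reads "Any observed postoperative (any time from transfer from OR to discharge) myocardial ischemia or infarction". RBC transfusion has the same window. Death is an endpoint only as a component of the composite.

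Two endpoints differ. Infection reads "Postoperative (any time from transfer from OR to discharge) occurrence of any form infectious complication up to POD 30", which is two windows in one line. Stand-alone atrial fibrillation reads "Any occurrence of immediate postoperative atrial fibrillation", a window that does not run to discharge. Section 11.4.3.1 lists atrial fibrillation again with no window.

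Hospital stay is an endpoint in the same section, and a stay of 4.5 days or more scores in the composite. Section 5.3 cites, from earlier studies, "decreased hospital LOS, decreased ICU LOS, decreased STS MOMM". Section 11.4.1 places collection of the follow-up clinical variables before discharge. The later telephone call (Section 11.4.4, 4 weeks plus or minus 5 days) asks about well-being, "if there was any need for hospital readmission or emergency ward visit" and days in a facility. Readmission is the exception: its window is 30 days from surgery.

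**The concern.** A window that closes at discharge closes on something that happens after randomization and that treatment may change. Suppose the monitoring shortens stay and prevents nothing. Events that would have fallen in the last hospital day or two then fall at home and are not counted, more often in the intervention arm. The complication rates differ although the risks are equal.

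Section 6.2 makes it the primary objective to find the outcomes that diverge because of randomization, so that a larger trial can be designed around them. A ratio that partly reflects earlier discharge could steer both the choice of endpoint and the sample size of that trial. Section 15 has no method for unequal observation time.

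**Working it through.** The plan states no expected stay, event rate or effect size, so there is no figure to reproduce. The check has two parts.

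**Windows side by side**

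| Endpoint | Window | Depends on stay? |
|---|---|---|
| Stroke/TIA, MI/ischemia, RBC transfusion | OR transfer to discharge | Yes |
| Composite, including death | OR transfer to discharge | Yes |
| Infection | To discharge, and to day 30 | Unclear |
| Atrial fibrillation, stand-alone | Immediate postoperative | Mostly no |
| Readmission | 30 days from surgery | No |

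**Size if stay shortens and nothing is prevented**

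Assumptions, none from the documents:
- Lognormal stay with coefficient of variation 0.5; median stay (control/intervention) 5/4.5, 5/4 or 6/4 days.
- The same 30-day event risk in both arms: 5%, 10% or 20%.
- Event times either uniform over 30 days, or front-loaded (exponential, mean 4 days, cut at 30).
- Event time independent of stay.

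From the documents: 100 subjects randomized 1:1, about 50 per arm.

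Proportion counted = risk × P(event time < stay). With uniform timing this is close to risk × mean stay / 30, where mean stay = median × √(1 + 0.5²) = median × 1.118. For 5/4 days and 10% risk:
- Control: 0.10 × 5.59 / 30 = 1.86%
- Intervention: 0.10 × 4.47 / 30 = 1.49%
- Ratio: 4/5 = 0.80

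Simulation (2,000,000 draws per arm) at 10% risk:

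| Timing | Median stay (days) | Counted, control | Counted, intervention | Risk ratio | Events per 50 |
|---|---|---|---|---|---|
| Uniform | 5/4.5 | 1.87% | 1.67% | 0.89 | 0.1 |
| Uniform | 5/4 | 1.87% | 1.49% | 0.80 | 0.2 |
| Uniform | 6/4 | 2.24% | 1.51% | 0.67 | 0.4 |
| Front-loaded | 5/4.5 | 7.03% | 6.68% | 0.95 | 0.2 |
| Front-loaded | 5/4 | 7.05% | 6.32% | 0.90 | 0.4 |
| Front-loaded | 6/4 | 7.58% | 6.32% | 0.83 | 0.6 |

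The last column is the difference × 50. Over all risks the simulated ratio runs from 0.66 to 0.95. Risk cancels from the ratio, so the low end is 4/6 = 0.67 apart from simulation error. A second set of assumptions (log-SD 0.4, exponential event times with means 3, 6 and 10 days) gives 0.91, 0.87 and 0.85 for 5 v 4 days, and 0.86, 0.79 and 0.76 for 5 v 3.5 days. With a fixed 30-day window, or with equal stay, the expected ratio is 1.00.

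The nominal 5% two-sided rejection rate at 50 per arm becomes 5.0-6.8% over all scenarios. This uses a normal approximation, which is rough when an arm expects only one to a few events.

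**Composite**

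This is simplified to stay of 4.5 days or more plus one clinical event (10% risk, uniform timing, medians 5/4). The stay component alone is Φ(ln(median/4.5)/0.472), where 0.472 = √ln 1.25. That gives Φ(0.223) = 58.8% and Φ(−0.249) = 40.2%; the simulation gave 58.9% and 40.1%.

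| Version | Control | Intervention | Gap (points) |
|---|---|---|---|
| Stay component alone | 58.9% | 40.1% | 18.8 |
| Composite as written | 59.3% | 40.7% | 18.6 |
| Clinical event extended to 30 days | 63.0% | 46.1% | 16.9 |

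The window accounts for 18.6 − 16.9 = 1.7 points. A subject still in hospital at 4.5 days has already scored, so only events after discharge in subjects sent home sooner are lost.

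**The case against.** Several points on the other side are sound.

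- **Follow-up does not end at discharge.** Table 1 marks adverse event monitoring through the follow-up period, which Section 7.2.4 runs to the 4-week call. A death after discharge, and most strokes or infarctions, would meet the serious adverse event definition in Section 13.1.2. A reader might infer that such events are never recorded; the documents do not support that. What stands is narrower: nothing links those records to the efficacy endpoints.
- **No effect on stay is assumed for this trial.** Section 5.3 is background from other studies. If stay does not differ, the arms are compared fairly, although later events are still missed in both.
- **The numbers are small.** At 10% risk the spurious difference is 0.1 to 0.6 of an event per 50 subjects. That is slight for screening in a pilot and supports treating this as bias in an estimate, not as a false-positive problem.
- **Timing may not be independent of discharge.** If subjects who look unwell are kept longer, more events fall inside the stay and the ratio moves towards 1.
- **In-hospital events are better documented.** Section 7.4.1.2 relies on neurological assessment, imaging and biomarkers; a telephone report is weaker.

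Two further stronger readings fail. It is tempting to say that infection and atrial fibrillation are also counted only to discharge. Infection has contradictory windows, and stand-alone atrial fibrillation covers only the immediate postoperative period. It is also tempting to blame the window for a lower composite rate, but the table shows that the stay component produces nearly all of it.

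**Conclusion.** The concern holds for stroke/TIA, MI/ischemia, RBC transfusion and the composite's clinical components, including death. Their window depends on an outcome that treatment may change, and any resulting bias favours the intervention. Its size is a spurious risk ratio of about 0.66 to 0.95 under assumed stays, event timings and independence between them, none of which the plan supplies. The effect on significance in this pilot is negligible. The cost falls on the next trial, which would inherit the estimate. The infection line must be reconciled whatever one thinks of the bias. For the composite, the window is a minor contributor and the length-of-stay component is the larger issue. The change is worth making because it is cheap and the protocol already uses a fixed window for readmission.

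**What to change.** - In Section 7.4.1.2, count death, stroke/TIA, MI, new atrial fibrillation, infection and new dialysis over one fixed window of 30 days from surgery in both arms. Use the same window for these events inside the composite.
- Reduce the infection line to that single window.
- State that adverse event data from the follow-up period feed these endpoints.
- Add these events, and the reason for any readmission or emergency visit, to the call in Section 11.4.4. Confirm reported events from available records.
- Align the call with the window. At 28 ± 5 days it can fall on day 23 to 33. Either make it on or after day 30, which fits the synopsis's description of a 30-day interview, or set the window no later than day 23.
- Report the composite also without its hospital-stay and PACU-stay components.
- Keep the to-discharge counts as descriptive. Label as in-hospital any measure that stays so, such as transfusion units and the creatinine component.

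The cost is protocol wording, a few questions on a call already planned for every subject, and some record checks. Some post-discharge events will be self-reported, and a few subjects may not be reached.
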